13.0 Provisions to Monitor the Data to Ensure the Safety of Subjects

A data and safety monitoring plan will be implemented by the PI to ensure that there are no changes in the risk/benefit ratio during the course of the study and that confidentiality of research data is maintained. Each member of the study team will meet with the PI and review confidentiality issues prior to having contact with research subjects.

The monitoring of adverse events will be ongoing throughout the study. Investigators and study personnel will meet regularly to discuss the study (study goals and modifications of those goals; participant recruitment and retention; progress in data coding and analysis; documentation, identification of adverse events or research participant complaints; violations of confidentiality) and address any issues or concerns at that time. Minutes will be kept for these meetings and will be maintained in the study regulatory folder. Any instances of adverse events will be immediately reported to MUSC's IRB using the standard forms and procedures that have been established by the IRB. The yearly IRB renewal for this study will include a summary report of the Data and Safety Monitoring Plan findings from the prior year.

Due to the minimal risk of the study, and because no serious adverse events are expected, there will be no specific safety endpoints. However, adverse events and unanticipated problems will be immediately reported. The laryngologist, will review adverse events and unanticipated problems and provide an expert assessment as to the probability of the event/problem being related to the experimental procedures. This will be determined mainly by the temporal relationship with the procedure, the environment, and the subject's clinical state.

14.0 Withdrawal of Subjects

In the cases where subject should develop a health condition non-related to the study protocol, a study team member would discuss with them that it is not appropriate at this time, given medical concerns, that they continue with the study intervention. The laryngologist, [name], would be informed of the situation and the medical team would make sure that the participant receives appropriate medical assistance.

Subjects are allowed to withdraw at any time, they are clearly advised that this will not affect their medical care or any aspects of their treatment.

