10.0 Study Design / Methods

Overview

After being enrolled in the study, treatment-seeking patients with a diagnosis of presbyphonia will undergo baseline respiratory assessments including spirometry and respiratory muscle strength measures as well as voice recordings (acoustic assessments). Participants will then be blocked-randomized (based on their MIP and MEP) to one of three groups using a 3-parallel arm design: (2 experimental groups and 1 control group), using a 3-parallel arm design: 1) inspiratory training (IMST) (experimental group), 2) expiratory training (EMST) (experimental group), or 3) standard of care (VFE) (control group), delivered four times (see table 1 for participant timeline). The sessions will occur on the same days as the participants' scheduled voice therapy sessions when possible. Participants will be asked to practice their respective exercises for 10 minutes, twice daily, seven days a week during the duration of the study. A final assessment session, after the 4th therapy session, will mirror the baseline measures. Participants will receive a monetary compensation of \$20 for each study visit, for a maximum of \$80 for the whole study. Payments will be made via cash. Outcomes that rely on subjective judgment (visual ratings of

videostroboscopy and perceptual judgments of voice quality) will be rated by trained judges (SLPs) blinded to the group assignment. [**Note**: Long-term follow-up will not be conducted. This study's focus is on the mechanistic effects of the intervention; future studies, given positive outcomes from this study, will explore the effectiveness and long-term effects.]

Table 1: Participant Timeline

Visit 1	Visit 2	Visit 3	Visit 4
Baseline assessment session			
Therapy session 1	Therapy session 2	Therapy session 3	Therapy session 4
			Final assessment session

Patient Participants

Standard of Care Assessments (Procedures being performed already for diagnostic purposes)

- Laryngeal imaging: prior to the examination, the laryngologist will administer topical lidocaine and neosynepherine in a spray to one of the nasal cavities. The laryngologist then passes the camera through the nose to examine the vocal folds. The participant will be asked to sustain phonation on the vowel /i/ for at least 3 seconds and to repeat with pitch and loudness variations.

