Firstly, the medical chart of the participant will be reviewed to obtain the following information: height and weight. This information will be used to perform the respiratory and muscle pressure assessments. The medical chart will also be used to track the speech therapy appointments, since research visits will take place on the same days. Spirometry assessments will take place at baseline and after the fourth intervention session. Muscle pressure testing and acoustic assessments will be conducted at baseline and before and after each intervention session.

Spirometry: Prior to the tasks, the participant will put on a nose clip and make sure that the lips are well sealed around the tube with no air is escaping. They will be asked to breathe normally, and then take a full inspiration and blow out with force during at least 6 seconds, in the spirometer. Those maneuvers will be repeated at least three times, to verify test reliability. No more than eight repetitions should be needed(47). The participant is seated to reduce risks of fall.

• Muscle pressure (maximum inspiratory pressure-MIP- and maximum expiratory pressure-MEP):

- o MIP: the participant is instructed to exhale slowly and completely, seal lips firmly around the mouthpiece, and then breathe in forcefully. The PI will note the largest negative pressure sustained for at least one second on the pressure gauge. The participant will rest for about one minute and then repeat the maneuver up to 4 additional times (with the goal of matching the highest 2 trials within 10 cmH₂O)(48).
- o MEP: the participant is instructed to inhale slowly and completely, seal lips firmly around the mouthpiece, and then breathe out forcefully. The PI will note the largest positive pressure sustained for at least one second on the pressure gauge. The participant will rest for about one minute and then repeat the maneuver up to 4 additional times (with the goal of matching the highest 2 trials within 10 cmH₂O) (48).

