12.0 Data Management

Data Analysis Plan

Demographic characteristics will be compared across the 3 intervention groups, using a RxC contingency table method for categorical variables (gender, smoking history, voice use, racial and ethnic category) and a one-way ANOVA for continuous variables (age, weight, height). Baseline characteristics will be compared across the 3 intervention groups using a Kruskal-Wallis one-way analysis of variance by ranks for ordinal data (GFI, RSI, and VHI scores), a RxC contingency table for categorical variables (glottal gap shape, free edge contour, vertical level, phase closure) and a one-way ANOVA for continuous variables. Aim 1: To assess the effects of respiratory training on voice and respiratory outcomes in patients with presbyphonia. Data will be analyzed on an intention-to-treat basis using multifactor repeated measures generalized linear regression. Distributional assessment will be made for each outcome to confirm optimal distributional assignment and potential need for outcome transformation (i.e. log link). In the model, the repeated factor is time, which has two levels (pre- or post-intervention) and the independent factor is the intervention, which has three levels (IMST, EMST, VFE). In the case of a significant between-subjects effect, multiple comparison tests will be conducted to determine which groups differ. The post-hoc analysis will be done using Tukey's honestly significant difference (offering protection against type I error without being too conservative). Spearman and Person correlations will be calculated to establish inter and intrarater reliability. Aim 2: To identify profiles of presbyphonic patients that would benefit the most from respiratory training. Logistic regression will be conducted to predict which patients improved following inspiratory training and which patients improved following expiratory training, based on their baseline clinical characteristics. Two outcome variables will be indicative of meaningful clinical improvement: 1) MPT (to measure function), and 2) GFI (to measure patient perception of function). Meaningful clinical improvement will be defined by an increase of at least 4 seconds in MPT or a decrease of at least 4 points in GFI score. Participants will be dichotomized as having meaningful clinical improvement, or not, based on these outcomes. Predictors will include MIP, MEP, maximum SPL, breaths per minute, FVC, FEV1, and P_s. These measures were chosen because they are directly influenced by the integrity of the respiratory system.

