Respiratory training: Respiratory training will be done in a sitting position, in a chair with arms and without wheel to avoid falls in the case where the participant would feel dizzy or light-headed. Health screening by [name] will be conducted to assess suitability for the training. To reduce risks of adverse events, patients that present with any pathology that would put them at risk when undergoing respiratory training will be excluded. This decision will be made by [name] based on the patient's history and clinical evaluation.

Version #11; 01/16/2019

During the study, patients will be asked to report and log in their journal any adverse events they are experiencing while conducting the respiratory training. Safety data will be monitored closely by the research team (see Data and Safety Monitory Plan) and a decision to stop treatment will be made if a participant presents with health concerns, as judged by the study team members and/or [name]. In cases of slight discomforts, the participants will be invited to take a break from the training and to breathe normally until the discomfort passes before resuming the exercises.

Incidental findings: Spirometry and muscle pressure evaluations are screening tests and therefore no diagnosis will be made based on the patients' performance.

Risks associated with randomization: Prior to being enrolled in the study, the patient will be clearly advised of the risks associated with randomization and the possibility that he or she may not be randomized to an experimental group. Participants will also be warned that the experimental treatments may not be proven to be effective.

Unknown risks: Study data and adverse events will be closely monitored by study personnel throughout the study.

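### The only final assessment is tied to completing the 4th therapy session, so participants whose study intervention is stopped early have no scheduled post-treatment value, and the intention-to-treat analysis is not secured for them

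*Combined protocol and SAP*

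**What the plan says.** **Stopping.** Section 14.0 (Withdrawal of Subjects) begins "In the cases where subject should develop a health condition non-related to the study protocol". A study team member then tells the participant that it is not appropriate "that they continue with the study intervention", and the laryngologist is informed. Free withdrawal by the participant is a separate paragraph in the same section. Section 15.0 (Protections Against Risk, respiratory training) says that "a decision to stop treatment will be made if a participant presents with health concerns, as judged by the study team members" and/or a named clinician. Neither section says what happens to later assessments.

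**Assessment.** Section 10.0 (Overview) states: "A final assessment session, after the 4th therapy session, will mirror the baseline measures". Table 1 puts that session in the visit 4 column. Under Experimental Assessments, "Spirometry assessments will take place at baseline and after the fourth intervention session", while "Muscle pressure testing and acoustic assessments will be conducted at baseline and before and after each intervention session". No calendar window or early-termination assessment is given.

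**Analysis.** Section 12.0 (Data Analysis Plan, Aim 1) states: "Data will be analyzed on an intention-to-treat basis". The model is a repeated measures generalized linear regression in which time has two levels, before and after the intervention. No rule is given for a missing post value. The only allowance for loss is in the Sample Size Justification: 15 needed per group, an estimated 10% dropout rate, and up to 16 recruited.

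**The concern.** An intention-to-treat analysis needs outcome data on everyone randomised, including those who stop treatment. Here the post value depends on reaching session 4. Someone stopped at visit 2 or 3 does not reach that point as the schedule is written, and no other time is set for measuring them.

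If such participants drop out of the analysis, each training arm is represented by those who could carry on with training. Stops under section 15.0 may plausibly be more frequent with inspiratory or expiratory training, because only those arms carry the training risks that the section describes. A contrast among completers could then favour training. With 16 per arm, each stop is 1/16 = 6.25% of an arm.

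**Working it through.** **1. What a stopped participant has under the plan as written**

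| Outcome | Values up to the stop | Scheduled post value after an early stop |
|---|---|---|
| Spirometry | Baseline only | None |
| MIP, MEP | Baseline and around each session attended | None |
| Study acoustic measures, including longest sustained /a/ | Baseline and around each session attended | None |
| Voice measures from standard of care (section 4.0) | Standard-of-care assessment | No date set |

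The section 12.0 model has only a pre and a post level, so it does not use the interim values in rows 2 and 3.

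**2. The plan's own sample size**

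Inputs from the Sample Size Justification: d = 0.90, power 80%, alpha 0.10, sidedness not stated.

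- Normal approximation, two-sided: n = 2 × (1.645 + 0.842)² / 0.90² = 15.3 per group, rounded up to 16. Power at 15 is 79.4%. The stated 15 is reproduced closely.
- One-sided, the same formula gives 12, so the stated figure fits a two-sided test.
- Exact t test, two-sided: 77.6% at 15 per group and 80.0% at 16.
- After the plan's own 10% loss: 16 × 0.9 = 14.4, already below 15. There is no room for further losses through stops.

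**3. Illustration of size**

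Assumptions, none of them from the documents: k of 16 stop in one training arm and none in the control arm; completers show the plan's d = 0.90; those stopped keep a fraction g of that gain.

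All-randomised effect = 0.90 × [(16 − k) + k × g] / 16. Overstatement by completers = 0.90 × k × (1 − g) / 16.

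The power column is the exact t test, two-sided alpha 0.10, d = 0.90 among those observed, 16 − k against 16.

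| k | All-randomised d, g = 0 | Overstatement, g = 0 | g = 0.5 | g = 1 | Power |
|---|---|---|---|---|---|
| 0 | 0.90 | 0 | 0 | 0 | 80.0% |
| 1 | 0.84 | 0.06 | 0.03 | 0 | 78.8% |
| 2 | 0.79 | 0.11 | 0.06 | 0 | 77.5% |
| 3 | 0.73 | 0.17 | 0.08 | 0 | 75.9% |
| 4 | 0.68 | 0.23 | 0.11 | 0 | 74.2% |

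Example, k = 2 and g = 0: 0.90 × 14/16 = 0.79, and 0.90 − 0.79 = 0.11.

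The loss of power is modest. What matters more is the possible shift in the estimate.

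**4. The two stopping passages side by side**

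- Section 14.0: conditions not related to the protocol; a study team member speaks to the participant and the laryngologist is informed.
- Section 15.0: health concerns in the setting of respiratory training, without regard to cause; judged by team members and/or a named clinician.
- Section 13.0: the laryngologist gives the expert view on whether an event is related to study procedures.

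Scope and decision roles differ. A condition unrelated to the protocol that arises during training fits both passages.

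**The case against.** The strongest reply is that silence is not exclusion. Section 14.0 stops the intervention and deals with voluntary withdrawal separately. A reader might infer that a stopped participant never reaches the final assessment, but no passage says so. This stands: what the documents support is that no assessment is scheduled for these participants.

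A reader might also infer that safety stops will be concentrated in the training arms. The documents do not establish that. The section 14.0 sentence concerns conditions not related to the protocol, which on their face give little reason for imbalance. Spirometry and muscle pressure testing carry dizziness and syncope risks in all arms. At-risk patients are screened out, a load that is too hard is lowered, slight discomfort leads to a pause, and section 13.0 expects no serious adverse events. Imbalance is plausible through section 15.0, but no rate is given.

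Nor is every outcome lost. Interim MIP, MEP and acoustic values exist up to the stop, and all arms carry on with standard voice therapy. Those interim values do not enter the two-level model, however, spirometry has none, and no standard-of-care assessment is dated for someone who stops.

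It would also be too strong to say that stopped participants go unobserved for safety: adverse events are monitored throughout and reported to the IRB under section 13.0, and section 14.0 provides for medical assistance.

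Finally, the illustrated shift is small against sampling error. The standard error of d with 16 per arm is about √(2/16) = 0.35 SD, so 0.06 to 0.23 SD is roughly 0.16 to 0.64 of one standard error. That supports treating this as an inexpensive improvement to a pilot.

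**Conclusion.** The point holds in a limited form. The final assessment is defined only by completion of session 4, no assessment is scheduled after an early stop, and the two-level model has no rule for a missing post value. Intention-to-treat is therefore promised but not secured for these participants. To say that it is not delivered would go too far: a likelihood-based repeated measures fit could keep baseline-only participants under missing at random. The plan does not specify that, and stopping because of intolerance would strain the assumption.

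Under the assumed 1 to 4 stops of 16 in one training arm, a completers-only contrast overstates d = 0.90 by 0.06 to 0.23 SD if stopped participants gain nothing, by 0.03 to 0.11 if they keep half, and by 0 if they keep all. The result rests on the assumed stop numbers and on stops falling in one arm only. The 4-second change in maximum phonation time should not be used to express this in seconds, because it is the Aim 2 threshold for individual improvement and not an expected mean gain.

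**What to change.** - **Section 10.0 (Overview, Table 1 and Experimental Assessments):** schedule the final assessment at the calendar time visit 4 would have taken place, for every randomised participant who has not withdrawn consent, whether or not training continued. Any assessment not suitable for that participant is left out.
- **Section 14.0:** state that stopping the study intervention is not withdrawal from study assessments, and record the reason for each stop by arm.
- **Section 12.0:** include all randomised participants in the Aim 1 model, and say how a post value that is still missing is handled.
- **Sections 14.0 and 15.0:** the sponsor should reconcile the two descriptions of stopping for health reasons, which differ in scope and in who decides. No clinical stopping rule is proposed here.

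The cost is mainly wording, plus a few additional assessment visits. All arms continue standard voice therapy, and all data collection is at one site, so some of these visits may coincide with ones already planned. A few participants will have partial respiratory data.

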15.0 Risks to Subjects

Potential Risks

Risks to subjects consist of 1) loss of confidentiality and 2) adverse events related to spirometry and muscle pressure testing 3) adverse events related to the experimental interventions (inspiratory and expiratory training) 4) incidental findings 5) risks associated with randomization and 6) unknown risks. There are no known risks are associated with acoustic assessment of voice.

Loss of confidentiality: The study will involve data collection from human subjects and is therefore subject to the risk of loss of confidentiality.

Spirometry and muscle pressure testing: Participants may feel the need to cough or may feel short of breath and/or dizzy during or after the test. There is a risk of syncope during the forced vital capacity (FVC) measurement.

Inspiratory training: Risks of discomfort, dizziness and light-headedness related to hyperventilation(53). The participant may feel short of breath or notice a pulse rate increase. Inspiratory training generates a

negative pressure in the thorax and for this reason it could aggravate conditions such as a pneumothorax, a middle ear pathology (such as a tympanic membrane rupture) or an acute unresolved sinusitis. Thus, patients with any diseases that are judged by the physician to be at risk of being exacerbated by the inspiratory training intervention will be excluded from study participation.

Expiratory training: During the expiratory training exercises, the patient has to generate sufficient expiratory effort to open a threshold valve and allow air to flow. The action increases the intraoral and intrathoracic pressures and has been compared to a sub-maximal Valsalva maneuver (54), which has been associated with blood pressure, heart rate changes and abnormal cardiac findings (55). However, expiratory training is not comparable to a typical Valsalva maneuver for two reasons: 1) the duration of the isometric muscle contraction during expiratory training is of approximately 2 seconds, which is much shorter than during a typical Valsalva maneuver (15-20 seconds) (54, 56); 2) during expiratory training, complete closure of the glottis rarely occurs, and when it does it is very briefly (54). Laciuga et al. (54) tested the effect of expiratory training on young health adults and found no acute changes in cardiovascular response (heart rate, blood pressure, oxygen saturation) and no adverse events following a session of 25 expiratory training trials. However, expiratory training is not recommended in older patients with certain cardiovascular disease or with untreated hypertension (18). Thus, patients with any diseases that are judged by the physician to put the patient at risk will be excluded from participating in this study.

Expiratory training is currently used in clinics and in research with various patient populations of the same age group as patients with presbyphonia, including patients with Parkinson's disease, multiple sclerosis and subacute stroke, as well as sedentary elderly participants (18, 30, 53, 57). No serious adverse events have been reported in the literature. Nonetheless, it is suggested that patients be cleared by a physician before undergoing expiratory training. We will follow this recommendation.

Incidental findings: Spirometry and muscle pressure evaluations are screening tests and therefore no diagnosis will be made based on the patients' performance.

Risks associated with randomization: This study's goal is to test the effectiveness of two types of intervention (inspiratory training and expiratory training) and to compare them to usual care received by voice patients when working with SLPs (voice exercises only). There is a chance that undergoing respiratory training may be less effective than using the additional time to work on voice exercises.

Unknown risks: Respiratory training has never been tested on patients with presbyphonia. The results of this combination are unknown. Although unlikely, there is a slight risk that unforeseen adverse events could result from this combination.

Protections Against Risk

Loss of confidentiality: Protection against the loss of confidentiality will be diminished by 1) completing study aims at one data collection site, 2) minimizing the participants involved to only those needed to accomplish the study aims (see sample size justification above), 3) de-identifying data at the earliest opportunity, and 4) maintaining stored data in locked/password protected locations whose access is restricted to members of the study team. All data collection and study activities will be conducted at MUSC. The patient subject sample will include up to 48 patients referred for a videostroboscopy within the scope of their usual care at MUSC and who meet the inclusion criteria. The sample will be limited to the MUSC site because historical accruals have been shown sufficient to meet power (see participant section above). Six participant raters will be recruited from SLPs who have experience with voice disorders. An alphanumeric identifier will be used instead of patient participant name and rater participant name at the earliest possibility. In order to ensure participant's confidentiality, database entry will be password protected and study documents will be maintained in a locked cabinet in the PIs locked office. Patient identity will also be protected by confidentiality policies and procedures already in place at the MUSC site. A participant may withdraw from the study at any time without penalty or prejudice.

Spirometry and muscle pressure testing: If the patient-participant manifests signs of discomfort or dizziness, the spirometry or muscle pressure testing maneuver will be interrupted following the American Thoracic Society's (ATS) recommendations(47). Stopping the maneuver will avoid a syncope, which could follow due to the interruption of venous return to the thorax during prolonged exhalation. As a precaution, all assessments will be done in a sitting position, in a chair with arms and without wheels to prevent falls.

Respiratory training: Respiratory training will be done in a sitting position, in a chair with arms and without wheel to avoid falls in the case where the participant would feel dizzy or light-headed. Health screening by [name] will be conducted to assess suitability for the training. To reduce risks of adverse events, patients that present with any pathology that would put them at risk when undergoing respiratory training will be excluded. This decision will be made by [name] based on the patient's history and clinical evaluation.

Version #11; 01/16/2019

During the study, patients will be asked to report and log in their journal any adverse events they are experiencing while conducting the respiratory training. Safety data will be monitored closely by the research team (see Data and Safety Monitory Plan) and a decision to stop treatment will be made if a participant presents with health concerns, as judged by the study team members and/or [name]. In cases of slight discomforts, the participants will be invited to take a break from the training and to breathe normally until the discomfort passes before resuming the exercises.

Incidental findings: Spirometry and muscle pressure evaluations are screening tests and therefore no diagnosis will be made based on the patients' performance.

Risks associated with randomization: Prior to being enrolled in the study, the patient will be clearly advised of the risks associated with randomization and the possibility that he or she may not be randomized to an experimental group. Participants will also be warned that the experimental treatments may not be proven to be effective.

Unknown risks: Study data and adverse events will be closely monitored by study personnel throughout the study.

